6.2.1.2 Vaccination Visits (Days 1 and 29)

Prior to receipt of the study vaccine, participants must complete:

1. An interview to review the following:
 - a. Current symptoms and AEs
 - b. Risks of recent exposure to COVID-19 and for symptoms of COVID-19
 - c. Concomitant medications, vaccinations, and procedures
2. A complete physical examination
3. Pregnancy testing (if the participant is a woman of childbearing potential). Blood sampling may be performed for pregnancy test if urine testing is not permitted by site policy.
4. A blood draw for safety laboratories, immunogenicity assessments, and archival samples (refer to [Appendix 1](#) for the Schedule of Assessments)
5. VS measurements (HR, respiratory rate, blood pressure, and body temperature)

The following should also be considered/undertaken before receipt of the study vaccine:

6. The participant should be randomized if the participant remains eligible, if randomization has not been done previously (Day 1).
7. If the participant remains eligible for the study vaccination, the study vaccine assigned should be administered by the vaccine administrator.
8. The participant should be observed post-vaccination for at least 30 minutes and until stable. After each study vaccine administration, vital signs should be checked, and repeat vital signs should be taken if clinically indicated.
9. The Diary Card should be distributed to the participant, and the participant should be trained on completion procedures and requirements for the Diary Card.

If the participant is screened and enrolled on the same day (Day 1), Screening Visit procedures will not be repeated.

6.2.1.3 Post-vaccination Visits on Days 4, 8, 32, and 36

At these visits, participants will have:

1. An interview to review the following:
 - a. AEs
 - b. Risks of recent exposure to COVID-19 and for symptoms of COVID-19
 - c. Concomitant medications, vaccinations, and procedures
2. A review of Diary Card compliance
3. A symptom-directed physical examination
4. A blood draw for safety

5. VS measurements taken (HR, respiratory rate, blood pressure, and body temperature)

6.2.1.4 Post-vaccination Visits on Days 15 and 43

At these visits, participants will have:

1. An interview to review the following:
 - a. AEs
 - b. Risks of recent exposure to COVID-19 and for symptoms of COVID-19
 - c. Concomitant medications, vaccinations, and procedures
2. A symptom-directed physical examination
3. A blood draw for immunogenicity assessments and archival samples
4. VS measurements taken (HR, respiratory rate, blood pressure, and body temperature)

6.2.1.5 Post-vaccination Visit on Day 57

At this visit, participants will have:

1. An interview to review the following:
 - a. AEs
 - b. Risks of recent exposure to COVID-19 and for symptoms of COVID-19
 - c. Concomitant medications, vaccinations, and procedures
2. A symptom-directed physical examination
3. A blood draw for safety laboratories, immunogenicity assessments, and archival samples (refer to [Appendix 1](#) for the Schedule of Assessments)
4. VS measurements taken (HR, respiratory rate, blood pressure, and body temperature)

6.2.1.6 Post-vaccination Visits on Days 119, 209, and 299

At these visits, participants will have:

1. An interview to review the following:
 - a. AEs
 - b. Risks of recent exposure to COVID-19 and for symptoms of COVID-19
 - c. Concomitant medications, vaccinations, and procedures
2. A symptom-directed physical examination
3. A blood draw for immunogenicity assessments and archival samples (refer to [Appendix 1](#) for the Schedule of Assessments)
4. VS measurements taken (HR, respiratory rate, blood pressure, and body temperature)

6.2.1.7 Final Visit on Day 394/Early Termination Visit

At this visit, participants will have:

1. An interview to review the following:
 - a. AEs
 - b. Risks of recent exposure to COVID-19 and for symptoms of COVID-19
 - c. Concomitant medications, vaccinations, and procedures

2. A complete physical examination
3. A blood draw for immunogenicity assessments and archival samples
4. VS measurements taken (HR, respiratory rate, blood pressure, and body temperature)
5. Counseling about long-term follow-up for SARS-CoV-2 infection (Early Termination [ET] visit)

6.2.2 Cohort B Visits

The Schedule of Assessments for Cohort B is located in [Appendix 2](#).

Participants in Cohort 2 are followed for 12 months post study vaccine until Day 366. Study vaccine is administered on Day 1 where safety and immunogenicity assessments are also performed prior to administration of the study vaccine. Clinic visits including safety laboratories should occur 3, 7, and 28 days post-vaccination (Days 4, 8, and 29, respectively). Clinic visits including blood collection to measure the participants immune response to the study vaccine on Days 15, 29, 91, 181, 271, and 366 (Final Visit).

6.2.2.1 Screening

At Screening, individuals willing to participate in the study will:

1. Review and provide informed consent
2. Have an interview to review the following:
 - a. Medical history
 - b. Current symptoms
 - c. Risks of recent exposure to COVID-19 and for symptoms of COVID-19
 - d. AEs
 - e. Concomitant medications, vaccinations, and procedures
 - f. Availability for study procedures
3. Have a complete physical examination
4. Take a pregnancy test (if the participant is a woman of childbearing potential). Blood sampling may be performed for a pregnancy test if urine testing is not permitted by site policy. A FSH test will be given to women suspected to be menopausal.
5. Undertake a blood draw for Screening laboratories (refer to [Appendix 2](#) and [Appendix 3](#) for list of Screening assessments)
6. Have their VS measurements taken (HR, respiratory rate, blood pressure, and body temperature)
7. Have their height and weight measurements taken.

The information gathered from this interview and the assessments will be evaluated against inclusion/exclusion criteria to determine study eligibility.

6.2.2.2 Vaccination Visit on Day 1

Prior to receipt of the study vaccine, participants must complete:

1. An interview to review the following:
 - a. Current symptoms and AEs
 - b. Risks of recent exposure to COVID-19 and for symptoms of COVID-19

- c. Concomitant medications, vaccinations, and procedures
2. A complete physical examination
3. Pregnancy testing (if the participant is a woman of childbearing potential). Blood sampling may be performed for pregnancy test (if urine testing is not permitted by site policy).
4. A blood draw for safety laboratories, immunogenicity assessments, and archival samples
5. VS measurements (HR, respiratory rate, blood pressure, and body temperature)

The following should also be considered/undertaken before receipt of the study vaccine:

6. The participant should be randomized if the participant remains eligible, if randomization has not been done previously.
7. If the participant remains eligible for study vaccination, the study vaccine assigned should be administered by the vaccine administrator.
8. The participant should be observed post-vaccination for at least 30 minutes or until stable.
9. The Diary Card should be distributed to the participant, and the participant should be trained on completion procedures and requirements for the Diary Card.

If the participant is screened and enrolled on the same day (Day 1), Screening Visit procedures will not be repeated.

6.2.2.3 Post-vaccination Visits on Days 4 and 8

At these visits, participants will have:

1. An interview to review the following:
 - a. AEs
 - b. Risks of recent exposure to COVID-19 and for symptoms of COVID-19
 - c. Concomitant medications, vaccinations, and procedures
2. A review of Diary Card compliance
3. A symptom-directed physical examination
4. A blood draw for safety laboratories
5. VS measurements taken (HR, respiratory rate, blood pressure, and body temperature)

6.2.2.4 Post-vaccination Visits on Days 15, 29, 91, 181, and 271

At these visits, participants will have:

1. An interview to review the following:
 - a. AEs
 - b. Risks of recent exposure to COVID-19 and for symptoms of COVID-19
 - c. Concomitant medications, vaccinations, and procedures
2. A symptom-directed physical examination
3. A blood draw for immunogenicity assessments and archival samples (refer to [Appendix 2](#) for the Schedule of Assessments)
4. A blood draw for safety (Day 29 only)
5. VS measurements taken (HR, respiratory rate, blood pressure, and body temperature)

6.2.2.5 Final Visit Day 366/Early Termination Visit

At this visit, participants will have:

1. An interview to review the following:
 - a. AEs
 - b. Risks of recent exposure to COVID-19 and for symptoms of COVID-19
 - c. Concomitant medications, vaccinations, and procedures
2. A complete physical examination
3. A blood draw for immunogenicity assessments and archival samples
4. VS measurements taken (HR, respiratory rate, blood pressure, and body temperature)
5. Counseling about long-term follow-up for SARS-CoV-2 infection (ET visit)

6.2.3 Unscheduled Visits (both Cohort A and B)

Unscheduled visits include visits for specific safety issues and/or evaluation of possible COVID-19. These visits will ideally be performed in person; however, if local restrictions (e.g., lockdown) prevent this, they may be performed by telemedicine/telephone visit or home visit. Required procedures at these visits include AE and concomitant medication, vaccination, and procedure collection. For participants evaluated for COVID-19, samples should be collected for SARS-CoV-2 testing. Should the visit occur in person, the visit should also include evaluation of VS, body temperature, pulse oximetry (if feasible), and a symptom-directed physical examination.

6.3 Safety Assessments

Safety assessments will include monitoring and recording of solicited and unsolicited AEs, MAAEs, AEs leading to discontinuation of the study vaccine/study withdrawal, SAEs, VS, and safety laboratory assessments.

6.3.1 Adverse Events

6.3.1.1 Definitions

6.3.1.2 Adverse Events

The Investigator is responsible for reporting all AEs that are observed or reported during the study, regardless of their relationship to the study vaccine or their clinical significance. AE collection will begin after the signing of informed consent; however, AEs that occur prior to the administration of first dose of the study vaccine (i.e., non-treatment-emergent AEs) will be listed separately in the CSR.

An AE is defined as any untoward medical occurrence associated with the use of a medicinal product in humans, whether or not considered related to the medicinal product.

An AE, therefore, can be any of the following:

- Any unfavorable and unintended sign (including an abnormal laboratory finding), symptom, or disease temporally associated with the use of a medicinal product, whether or not considered related to the medicinal product

- Any new disease or exacerbation of an existing disease (a worsening in the character, frequency, or severity of a known condition)
- Recurrence of an intermittent medical condition (e.g., headache) not present at baseline
- Any deterioration in a laboratory value or other clinical test (e.g., electrocardiogram [ECG], X-ray) that is associated with symptoms or leads to a change in study treatment or concomitant treatment or discontinuation from the study vaccine
- AEs that are related to a protocol-mandated intervention, including those that occur prior to administration of the study vaccine (e.g., Screening invasive procedures such as biopsies)

6.3.1.2.1 Serious Adverse Events

An SAE is defined as any event that:

- Results in death
- Is immediately life threatening
- Requires inpatient hospitalization or prolongation of existing hospitalization
- Results in persistent or significant disability/incapacity
- Is a congenital anomaly/birth defect

Important medical events that may not result in death, be life threatening, or require hospitalization may be considered SAEs when, based upon appropriate medical judgment, they may jeopardize the participant or may require medical or surgical intervention to prevent one of the outcomes listed in this definition. Examples of such medical events include allergic bronchospasm requiring intensive treatment in an emergency room or at home, blood dyscrasias or convulsions that do not result in inpatient hospitalization, or the development of drug dependency or drug abuse.

6.3.1.2.2 Suspected Unexpected Serious Adverse Reaction

A suspected unexpected serious adverse reaction (SUSAR) is any SAE wherein a causal relationship to the study vaccine is at least reasonably possible and wherein the nature or severity of the AE is not consistent with the Reference Safety Information in the most current version of the Arcturus IB.

6.3.1.2.3 Medically Attended Adverse Events

An MAAE is an AE that leads to an unscheduled visit (including a telemedicine visit) with an HCP (e.g., nurse, nurse practitioner, physician's assistant, physician). This would include visits to a study site for unscheduled assessments (e.g., rash assessment, abnormal laboratory follow-up, COVID-19) and visits to HCPs external to the study site (e.g., urgent care, primary care physician).

- Routine study visits will not be considered medically attended visits.
- AEs observed in the immediate 30-min post-vaccination observation period will be regarded as MAAE if:
 - Treatment of the AE is required prior to discharge OR
 - Extension of observation is required due to clinical concerns or unstable clinical findings

Investigators will review unsolicited AEs for the occurrence of any MAAEs. All MAAEs must be reported in the eCRF.

6.3.1.2.4 Adverse Events Leading to Discontinuation of Study Vaccine/Study Withdrawal

Any AE that leads to discontinuation of the study vaccine and/or withdrawal from the study will be regarded as an AE leading to discontinuation from the study vaccine and/or study withdrawal. Investigators will review reasons for discontinuation from the study vaccine or study withdrawal and report this on the appropriate eCRF page.

6.3.1.2.5 Adverse Event of Special Interest

An adverse event of special interest (AESI), including both serious or non-serious events, is one of scientific and medical concern specific to the Sponsor's product or program, for which ongoing monitoring and rapid communication by the Investigator to the Sponsor is appropriate.

AESIs, as defined in the study protocol or associated documents, are required to be reported by the Investigator to the Sponsor immediately, no more than 24 hours after the Investigator's first knowledge of the event.

AESIs include myocarditis, pericarditis, and myopericarditis according to the Brighton Collaboration case definitions ([Sexson Tejtel 2021](#)). All participants should be instructed to report any acute chest pain, shortness of breath, palpitations, or other signs or symptoms of myocarditis or pericarditis occurring within 6 weeks after vaccination to site personnel as soon as possible (within 24 hours).

In addition to reporting requirements to the Sponsor, the Investigator must refer participants reporting symptoms of myocarditis or pericarditis to a cardiologist for evaluation and management. In the event that the participant is unable to be seen by a cardiologist within 24 hours, the participant should have an unscheduled visit within 24 hours, if medically stable, to evaluate the event and have cardiac markers drawn and a 12-lead ECG performed. A questionnaire will be provided to Investigators for case evaluation for any reported events. Cases of myocarditis and pericarditis will be followed until resolution of symptoms and abnormal test findings.

Cases of myocarditis and/or pericarditis occurring in temporal association with vaccination will be considered potentially related, unexpected and serious, and are subject to expedited reported requirements as outlined in Section [6.3.1.2.13](#).

6.3.1.2.6 Solicited Adverse Events

The term "reactogenicity" refers to selected signs and symptoms ("reactions") occurring in the hours and days following a vaccination. These signs and symptoms are collected as solicited AEs from participants by use of the Diary Cards for 7 consecutive days following each study vaccine administration.

The following solicited AEs are included in the Paper Diary:

- Solicited local AEs: Injection site erythema, injection site pain, injection site induration/swelling, and injection site tenderness

- Solicited systemic AEs: Arthralgia, chills, diarrhea, dizziness, fatigue, fever (categorized by measured body temperature), headache, myalgia, and nausea/vomiting

The occurrence of each of these solicited AEs is regarded as a study vaccine-related AE.

Also solicited from participants but not categorized as an AE is the use of antipyretics and analgesics to prevent or treat solicited AEs.

Solicited AEs are graded for severity according to scales defined in the US FDA's Center for Biologics Evaluation and Research's Guidance: Toxicity Grading Scale for Healthy Adult and Adolescent Volunteers Enrolled in Preventive Vaccine Clinical Trials ([DHHS 2007, Appendix 5](#)).

Solicited AEs may also lead to circumstances that warrant collection of the events as unsolicited AEs. This includes any solicited AE that leads to any of the following:

- A medically attended visit
- An SAE
- Discontinuation of the study vaccine
- Withdrawal from the study
- Any solicited AE that persists beyond 7 days after each study vaccine administration

Furthermore, should the site determine that the participant experienced and failed to enter a Grade 3 or Grade 4 solicited AE in the Diary then this Grade 3 or Grade 4 solicited AE should be entered as an unsolicited AE in the eCRFs.

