Primary Objectives and Primary Endpoints	
Objective 1: To describe the safety and reactogenicity of 3 investigational SARS-CoV-2 self-amplifying RNA vaccines
 
Endpoint 1: Safety will be summarized for each vaccination as the number and percentage of participants with the following:
 
 a. Any solicited local or systemic adverse event (AE) collected for 7 days after each study vaccination, which will be assessed by toxicity grade b. Any unsolicited AE collected for 28 days after each study vaccination, which will be assessed by severity and relationship to study vaccine c. Any medically attended adverse events (MAAEs), AEs leading to discontinuation from study vaccine/study withdrawal, or serious

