6.1.7 Diary Card Procedures

Paper Diary Cards will be distributed to participants at each study vaccination visit. They will be instructed to complete the Diary Card for 7 days post-vaccination. Compliance will be checked at the study visits that are conducted 3 and 7 days after each study vaccination. Diary Cards are source documents and should be collected on Day 8 (Cohort A and Cohort B) and Day 36 (Cohort A) visits and maintained in the participants' study files. Data from the diary card must be transcribed verbatim into the electronic data capture system.

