6.3.1.2.9 Assessment of Severity

Solicited AEs: The intensity of solicited AEs will be graded for severity as Grade 0, Grade 1 (mild), Grade 2 (moderate), Grade 3 (severe), or Grade 4 (potentially life threatening). The severity of solicited AEs will be assessed according to scales based on the US FDA toxicity grading scales for vaccine clinical studies, as shown in [Appendix 5](#).

Unsolicited AEs: The severity of unsolicited AE will be rated as mild, moderate, or severe using the following criteria:

Mild:

- These events require minimal or no treatment and do not interfere with the participant's daily activities.

OR

- An event usually transient in nature and generally not interfering with normal activities.

Moderate:

- These events result in a low level of inconvenience or concern with the therapeutic measures. Moderate events may cause some interference with normal functioning.

OR

- An AE that is sufficiently discomforting to interfere with normal activities.

Severe:

- These events interrupt a participant's usual daily activities and may require systemic drug therapy or other treatment. Severe events are usually incapacitating.

OR

- An AE that is incapacitating and prevents normal activities.

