7.5.3 Safety Analysis

Safety, reactogenicity, and safety laboratory assessments will be evaluated in the Safety set. Participants will be summarized according to the study vaccine that was received.

Descriptive statistics will be provided for each solicited AE and for each study vaccine group. Local and systemic AEs from Day 1 through Day 7 after each vaccination will be presented by severity cumulatively using a 5-point toxicity grading scale (Grades 0 through 4). Descriptive summary statistics will include counts and percentages of participants with the indicated endpoint.

Descriptive statistics will also be provided for abnormal hematology and chemistry laboratory values at Day 1 and at 3, 7 and 28 days following each dose of the study vaccine, including shifts in toxicity grading (DHHS 2007). Descriptive summary statistics will include counts and percentages of participants with the indicated endpoint.

Unsolicited AEs (including MAAEs, SAEs, and AEs leading to discontinuation/withdrawal) will be categorized according to MedDRA terms. Descriptive summary statistics (counts, percentages) will be provided for any unsolicited AE event in each study vaccine group.

Missing solicited AE diary data will not be imputed; missing AE dates will be handled according to the rules defined in the SAP.

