3.4.2.1 Adverse Events

An AE is defined as any untoward medical occurrence associated with the use of a medicinal product in humans, whether or not considered related to the medicinal product. Adverse event collection will begin after the signing of informed consent and continue through study exit. Adverse events that occur prior to the administration of first dose of the study vaccine (i.e., non-study vaccine-emergent AEs) will be listed separately in the CSR.

An adverse event of special interest (AESI), including both serious and non-serious events, include myocarditis, pericarditis, and myopericarditis.

Adverse events will be collected on two distinct CRFs to capture solicited AEs and unsolicited AEs.

Solicited AEs refer to selected signs and symptoms occurring in the hours and days following a vaccination. These will be collected from participants on paper diary cards for seven consecutive days following each study vaccine administration. The following solicited AEs are included in the paper diary:

- Solicited local AEs: Injection site erythema, injection site pain, injection site induration/swelling, and injection site tenderness
- Solicited systemic AEs: Arthralgia, chills, diarrhea, dizziness, fatigue, fever (categorized by measured body temperature), headache, myalgia, and nausea/vomiting

The occurrence of each of these solicited AEs is regarded as vaccine-related AE. Solicited AEs are graded for severity according to the 5-point scales defined in the US FDA's Center for Biologics Evaluation and Research's Guidance: *Toxicity Grading Scale for Healthy Adult and Adolescent Volunteers Enrolled in Preventive Vaccine Clinical Trials* (2007).

Unsolicited AEs are defined as any spontaneously reported or discovered AE. Unsolicited AEs will be collected in all participants who receive at least one dose of the study vaccine and are classified according to the following:

- Mild, moderate, or severe;
- Whether or not the AE was categorized as an SAE, a MAAE, and/or an AE leading to discontinuation of the study vaccine/ study withdrawal; and
- Whether or not the AE was related to the study vaccine or the study procedure in the judgment of the Investigator.

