4.1.1 Reporting Conventions

Participants in Cohort A and Cohort B will be analyzed independently for the final analysis, with distinct sets of tables, figures, and listings provided for each cohort.

For Cohort A, tables and figures will be summarized by sub-cohort (Sub-cohort A1 and Sub-cohort A2) and study vaccine group. Tables summarizing demographics and other baseline characteristics will also include columns for all participants combined within each sub-cohort. For Cohort B, tables and figures for each cohort will be summarized by study vaccine group. Tables summarizing demographics and other baseline characteristics will also include a column for all participants combined.

In general, all data collected and any derived data will be presented in participant data listings, for all enrolled participants. Listings will be ordered by site, participant number, cohort sub-group (Cohort A only), study vaccine group, and assessment or event date. The study vaccine group presented in listings will be based on the planned assignment, unless otherwise noted.

In general, continuous variables will be summarized to indicate the study population sample size (N), number of participants with available data (n), mean, SD, median, first (Q1) and third (Q3) quartiles, minimum, and maximum values. Categorical variables will be summarized by the population size (N), number of participants with available data (n), number of participants in each category, and the percentage of participants in each category. Unless otherwise noted, the denominator to determine the percentage of participants in each category will be based on the number of participants with available data. Select ordinal data may be summarized using both descriptive statistics and counts and percentages of participants in each category, as appropriate.

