4.6 Safety Evaluation

Safety analysis will be carried out for the SS, to include all participants who receive at least one dose of study vaccine. Participants who do not complete the study, for whatever reason, will have all available data up until the time of termination included in the analysis. For safety analysis presented by study visit, the baseline value will be defined as the last value reported prior to first study vaccine administration.

4.6.1 *Extent of Exposure*

Extent of exposure to study vaccine will be summarized for the SS by study vaccine group for each cohort. The total number of participants receiving each dose and the total number of doses will be presented for both cohorts. The interval of time between vaccinations will be presented in days for Cohort A only, and calculated as the date of second vaccine administration minus the date of first vaccine administration, plus one. Total number of doses and interval of time between vaccinations will be summarized using descriptive statistics.

4.6.2 *Adverse Events*

Study AEs that occur post vaccination will be summarized by study vaccine group for each cohort. Events reported with a partial onset date (e.g., month and year are reported but the day is missing) will be considered to be post vaccination if it cannot be confirmed that the event onset was prior to vaccination based on the available date entries.

Verbatim terms on case report forms will be mapped to preferred terms and system organ classes using the Medical Dictionary for Regulatory Activities (MedDRA, version 24.0). Injection site tenderness will only be coded to the lower-level term, as there is no PT of injection site tenderness (coded to a PT of injection site pain).

Solicited and unsolicited AEs will be summarized separately. The number of participants reporting solicited AEs within 7 days of each vaccination will be summarized by cohort (or Sub-cohort for Cohort A), study vaccine group, vaccination (for Cohort A), and toxicity grade for each day, as well as over the entire 7-day period. The duration of solicited adverse events occurring within 7 days of each vaccination will be summarized with descriptive statistics and the number of participants reporting AEs ongoing after 7 days will also be presented. The number of participants reporting unsolicited AEs within 28 days of each vaccination and through the end of the study will be presented.

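### Site-identified Grade 3/4 solicited reactions missing from the diary reach only the unsolicited AE tables, so the primary by-grade reactogenicity tables can understate known severe reactions

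*Protocol*

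**What the plan says.** - **Endpoint.** The first item of primary Endpoint 1 (Protocol synopsis, repeated in Table 2) is "Any solicited local or systemic adverse event (AE) collected for 7 days after each study vaccination, which will be assessed by toxicity grade".
- **Source.** Solicited reactions come from the paper diary (Protocol 6.3.1.2.6). Protocol 6.1.7 leaves the site no room to add to it: "Data from the diary card must be transcribed verbatim into the electronic data capture system". Protocol 7.5.3 adds: "Missing solicited AE diary data will not be imputed".
- **Routing rule.** For a Grade 3 or 4 solicited reaction that the site establishes but the participant did not enter, Protocol 6.3.1.2.6 states that "this Grade 3 or Grade 4 solicited AE should be entered as an unsolicited AE in the eCRFs".
- **Data structure.** SAP 3.4.2.1: "Adverse events will be collected on two distinct CRFs to capture solicited AEs and unsolicited AEs".
- **Analysis.** SAP 4.6.2: "Solicited and unsolicited AEs will be summarized separately". The list of AE tables in that section has no combined, flagged or sensitivity version. In the by-grade tables each participant is counted once, at the worst grade.
- **Scales.** Solicited reactions are graded 0 to 4 (Protocol Appendix 5). For the other stream, Protocol 6.3.1.2.9 says: "The severity of unsolicited AE will be rated as mild, moderate, or severe".

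**The concern.** The study tests no hypotheses, so the descriptive by-grade table is itself the primary reactogenicity result. A reader will take its Grade 3 and 4 rows as the count of severe solicited reactions. Under the rule, a severe reaction that the site has confirmed can be in the database and yet missing from that count. The unsolicited tables by system organ class and preferred term do not repair this, because they do not change the grade at which the participant appears in the solicited table. In groups this small, no Grade ≥3 reactions and one such reaction are different safety statements.

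**Working it through.** The plan gives no event rate, diary-omission rate or sample-size calculation, so there is no stated figure to reproduce.

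**1. Can an omitted event get back into the solicited table?** The diary is copied verbatim, missing diary data are not imputed, the two streams sit on separate CRFs, and the SAP summarises them separately. No step returns the event to the solicited tables.

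**2. Direction.** Suppose x participants in a group of n have a diary-recorded Grade ≥3 reaction, and one further participant has only an omitted one.
- If that participant has other diary data, the table shows x/n instead of (x+1)/n.
- If that participant has no diary data, the default in SAP 4.1.1 applies: "the denominator to determine the percentage of participants in each category will be based on the number of participants with available data". The table then shows x/(n−1). This never exceeds (x+1)/n, because xn ≤ (x+1)(n−1) reduces to x ≤ n−1.

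If the participant already has another Grade ≥3 diary entry, the any-Grade-≥3 count does not change. The omission therefore lowers that rate or leaves it alone.

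**3. Group sizes** (Protocol synopsis; SAP 3.1). Sub-cohort A1: 12/3 = 4 per vaccine. Sub-cohort A2: 24 × 3/4 = 18 on ARCT-154 and 24/4 = 6 on ARCT-021. Cohort B: 36/3 = 12 per vaccine.

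**4. Effect of one such participant when x = 0.** The change is 100/n points; intervals are exact Clopper-Pearson 95%.

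| Group | n | Diary only | With the event counted | Change (points) |
|---|---|---|---|---|
| A1, each vaccine | 4 | 0% (0–60.2) | 25.0% (0.6–80.6) | 25 |
| A2, ARCT-021 | 6 | 0% (0–45.9) | 16.7% (0.4–64.1) | 16.7 |
| B, each vaccine | 12 | 0% (0–26.5) | 8.3% (0.2–38.5) | 8.3 |
| A2, ARCT-154 | 18 | 0% (0–18.5) | 5.6% (0.1–27.3) | 5.6 |

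**5. How likely is it?** Assume a true Grade 3/4 rate p of 5–20% per participant and an omission probability m of 5–20%. Neither figure is in the documents. The chance that a group has at least one omitted Grade 3/4 participant is 1 − (1 − pm)^n:
- n=4: 1% to 15%
- n=6: 1.5% to 22%
- n=12: 3% to 39%
- n=18: 4% to 52%

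The rule covers only the omissions that the site discovers, so the chance of a known case is no higher than these values.

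**6. Is the loss selective by severity?** Assume 60% of participants have Grade 1/2 and 10% have Grade 3/4, a true severe share of 0.10/0.70 = 14.3%.
- Equal 10% omission: 0.09/(0.54 + 0.09) = 14.3%, unchanged.
- Severe omitted more often (20% against 10%): 0.08/(0.54 + 0.08) = 12.9%.
- Mild omitted more often (20% against 10%): 0.09/(0.48 + 0.09) = 15.8%.

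The severe share falls only if severe reactions are omitted more often than mild ones, and the documents do not say that they are.

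**The case against.** The strongest reply is that the routing rule removes nothing. A reaction absent from the diary, whatever its grade, was never in the solicited table. Without the rule that table would be identical and the safety database poorer. This stands. A reader might infer that the plan selectively strips the most severe events from the primary tables; the documents do not support that. The cause is diary omission at any grade, and the rule rescues the Grade 3/4 events. No such route is stated for omitted Grade 1/2 reactions.

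The events also stay visible in the 28-day unsolicited tables and in listings. Most Appendix 5 Grade 4 criteria involve an emergency visit or hospitalisation, so those events should also appear as medically attended or serious. A reader might further infer that a rerouted event loses its presumed relatedness. That is not established: Protocol 6.3.1.2.6 still calls it a solicited AE and treats every solicited AE as vaccine-related.

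Three further points stand in part. The percentage shifts are what any single event does in a small group, and the intervals overlap heavily. The unsolicited page may not hold the exact Appendix 5 grade. A table that adds site-identified severe events but no site-identified mild ones mixes two ascertainment methods by severity. These limit how an added table should be built and read. They do not answer the worst-grade count, which shows a lower grade than the one the site has confirmed.

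**Conclusion.** The concern holds as a reporting gap. The primary solicited by-grade tables can omit severe reactions already known to the study, and nothing in the SAP shows the reader that this has happened. The any-Grade-≥3 rate can only be too low or unaffected relative to what the site has confirmed. The shift of 5.6 to 25 points assumes planned group sizes, one affected participant, and no other Grade ≥3 event in that group. The frequency is unknown, and the probabilities in step 5 rest wholly on assumed ranges. The documents support neither a claim of selective loss nor a claim that the events vanish from the safety report. Events recorded in the diary and also collected as unsolicited (for example because they led to a medical visit) are not affected. Label: cheap improvement.

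**What to change.** Keep the eCRF routing and the diary-only by-grade tables. Add to SAP 4.6.2 one supplementary table, per vaccination and study vaccine group, of participants with any Grade ≥3 solicited reaction. Besides diary entries, it should count events on the unsolicited page that meet all of these conditions:

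- the term is a solicited one (matched at lower-level term for tenderness, which otherwise codes to injection site pain);
- onset is within 7 days of a dose;
- the event is rated severe, or known to be Grade 3 or 4;
- the diary has no Grade ≥3 entry for that term.

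Flag each event by source. Report Grade ≥3 combined unless the site recorded the Appendix 5 grade. State the denominator, because a participant without diary data drops out under the SAP default. A footnote should say that severe events have two ascertainment sources and milder ones only the diary.

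The cost is one derivation and one extra table, and the mixed ascertainment is the main downside. The SAP introduction allows amendment for Cohort A before database lock. If Cohort B is already unblinded, the table can be added there as a documented change in the clinical study report.
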